#### 9.4.4 Other safety analyses

All additional safety parameters such as laboratory parameters, vital signs, physical examinations and neurological examinations will be summarised and listed.

To analyse the trajectories of neurological examination over time, shift plots will also be presented by examining the proportion of neurological examination items which shift between every two consecutive examinations. For each item, the shift will be categorised into one of the three following groups:

- Shift up (improved): from abnormal to normal findings
- Shift down (worsening): from normal to abnormal findings
- No change: from abnormal to abnormal findings; or from normal to normal findings

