Thromboembolic events	
Thromboembolic events are considered an important potential risk considering the fact that supraphysiologically elevated procoagulant levels may be associated with an increased risk of venous thrombosis.
 
No thromboembolic events have been observed in the nonacog beta pegol clinical trial programme; see Section 6.4.2.3 of the investigator's brochure.
	Thromboembolic events are monitored closely.
Accumulation of polyethylene glycol (PEG) in the brain (choroid plexus) and in other tissues/organs after long-term treatment	
There has been no indication of PEG accumulation beyond steady state after nonacog beta pegol treatment non-clinically or clinically. The possible clinical consequences of potential PEG presence are currently unknown.
 
Potential effects of PEG accumulation are monitored closely.
	Long-term safety including potential effects of PEG accumulation in the choroid plexus and other tissues/organs are monitored in the clinical trials and post-marketing.
Trial procedures		
Intravenous (i.v.) injection	Wrong route of administration, e.g. intramuscular instead of intravenous.	Administration of trial product at sites are performed by trained staff. The previously treated patients and/or their caregivers have experience with i.v. injection and will be trained by site staff in use of the trial product.
Physical examination and body measurements	No risks are expected to be associated with standard physical examination. Burden (embarrassment, discomfort, distress) associated with examinations that are related to sexual development (e.g. in adolescents) can be expected.	As this assessment is performed by physicians familiar with the patient population, the burden is expected to be low.

Potential risk of clinical significance	Summary of data/rationale for risk	Mitigation strategy
Trial procedures (continued)		

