### **8.2.2.1      Neurological examination**

The following neurological examinations will be performed by the investigator (haematologist) or an appropriately trained designee under their supervision upon the outline specified in [Appendix 6](#) (this outline has been developed with guidance from a neurologist):

- General neurology including level of consciousness
- Cranial nerves in relation to sight including reaction to light, visual fields and acuity, and eye movements, facial sensation and movement, hearing, palate sound and tongue movement, and trapezius muscle function
- Tone of upper and lower extremity right and left
- Strength of upper and lower extremity right and left
- Reflexes of the biceps, triceps, knee and ankle right and left
- Sensory aspect of cold, pin prick, light touch and proprioception (toe up/down)
- Gait with regards to walking, running, on heels and toes, tandem (toe/heel walk), stand/hop on one leg/foot right and left, and Romberg sign
- Coordination and Fine Motor including finger-to-nose, rapid index finger tap and rapid finger movement right and left

Each aspect of the neurological examination will be categorised into normal, abnormal (pre-existing or new) or not evaluated.

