## **10.6 Appendix 6: Neurological examination checklist**

Unless otherwise stated, each aspect of the neurological examination will be categorised into normal, abnormal or not evaluated.

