5.6 Other safety analyses

All additional safety parameters such as laboratory parameters, vital signs and physical examinations will be summarised and listed.

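### Protocol 9.4.4 plots neurological shifts only between consecutive examinations, so a new deficit that persists shows as worsening only at onset; SAP 5.6 does not name these analyses

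*Protocol*

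**What the plan says.** Protocol 9.4.4 plans two presentations of the neurological data. One is general: "physical examinations and neurological examinations will be summarised and listed". The other is meant to show trajectories over time: "shift plots will also be presented by examining the proportion of neurological examination items which shift between every two consecutive examinations". Each item falls into one of three classes. Worsening is "Shift down (worsening): from normal to abnormal findings", improvement is the reverse, and the third class is "No change: from abnormal to abnormal findings; or from normal to normal findings". No comparison with baseline is specified.

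On recording, Protocol 8.2.2.1 states: "Each aspect of the neurological examination will be categorised into normal, abnormal (pre-existing or new) or not evaluated". The checklist in Appendix 6 states, unless otherwise noted for an item: "each aspect of the neurological examination will be categorised into normal, abnormal or not evaluated". The split into pre-existing and new is absent there.

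Protocol 2.4.1 lists as a potential risk "Accumulation of polyethylene glycol (PEG) in the brain (choroid plexus) and in other tissues/organs after long-term treatment", and describes its possible clinical consequences as unknown.

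SAP 5.6 consists of one sentence: "All additional safety parameters such as laboratory parameters, vital signs and physical examinations will be summarised and listed". The opening of the SAP says it is based on protocol version 1.0 of 21 January 2021. The current protocol is version 2.0 of 22 September 2021, and its table of changes records an update to the neurological examination and its analysis. SAP section 1 leaves specifications that it does not contain to a mock TFL, which is not among the documents.

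**The concern.** A display of trajectories should let the reader see whether patients end treatment worse than they began. Comparing each examination only with the one before it answers a different question: what changed in the latest interval. Because abnormal-to-abnormal is pooled with normal-to-normal, an item that becomes abnormal and stays abnormal leaves the worsening class after one panel.

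This matters because of the risk in Protocol 2.4.1. The protocol does not tie the neurological examination to PEG accumulation in so many words, but it is reasonable to read the examination as part of the monitoring of that risk. For a concern about cumulative exposure, persistent or accruing change from the pre-treatment state is the pattern of interest, and the only planned neurological shift display does not show it directly.

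The SAP adds a second problem. Its sentence on other safety analyses matches the corresponding protocol sentence except that neurological examinations are missing, and it specifies no shift plots. The supplied SAP therefore does not carry the analysis that the current protocol describes.

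**Working it through.** The documents give no figure on this point, so there is none to reproduce. The check applies the stated classes to item histories.

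**Inputs.** The classes come from Protocol 9.4.4. The examinations come from the flowchart in Protocol 1.2: Visits 1, 2 and 5, one mid-treatment visit, and Visit 10. The column alignment leaves it unclear whether the mid-treatment visit is Visit 7 or Visit 8; the result does not depend on which. Baseline is Visit 2. The item count comes from Appendix 6: 1 general + 10 cranial nerves + 4 tone + 4 strength + 4 sensory + 8 reflexes + 10 gait + 6 coordination = 47.

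**Step 1: classify item histories** (N normal, A abnormal, nc no change).

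| History at V1, V2, V5, mid, V10 | V1–V2 | V2–V5 | V5–mid | mid–V10 | Against V2, at V5 / mid / V10 |
|---|---|---|---|---|---|
| New at V5, lasting: N N A A A | nc | worse | nc | nc | worse / worse / worse |
| New at mid, lasting: N N N A A | nc | nc | worse | nc | nc / worse / worse |
| New at V5, transient: N N A N N | nc | worse | improved | nc | worse / nc / nc |
| Pre-existing: A A A A A | nc | nc | nc | nc | nc / nc / nc |
| Never abnormal: N N N N N | nc | nc | nc | nc | nc / nc / nc |

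In the last consecutive panel all five rows read no change. Against Visit 2, the two lasting deficits stand apart at Visit 10.

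**Step 2: can the panels be added up?** With complete data, the abnormal items at Visit 10 minus those at Visit 2 equal the sum of downward shifts minus the sum of upward shifts over the on-treatment intervals. The net count is therefore recoverable, but persistence is not. Take two items in one patient: X normal and Y abnormal at Visit 2.

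- Case 1: X runs N A N N over V2, V5, mid, V10, and Y stays abnormal. The new deficit resolves.
- Case 2: X runs N A A A, and Y runs A A N N. The new deficit lasts and an old finding improves.

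Both cases give the same consecutive panels: one worse, then one improved, then none. The net is 1 − 1 = 0 in both. Against Visit 2 at Visit 10, Case 1 shows 0 worse and 0 improved; Case 2 shows 1 worse and 1 improved. Pre-existing findings are plausible in this population: Protocol 2.1 describes arthropathy, muscular atrophy and deformity, and the checklist scores strength and gait.

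**Step 3: item-level illustration.** This is an assumption, not a forecast: one patient, 47 evaluated items, and one new lasting abnormal item in each of the three on-treatment intervals.

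- Consecutive rule: 1/47 = 2.1% worse in each of the three panels, a flat line.
- Against Visit 2: 1/47 = 2.1%, 2/47 = 4.3% and 3/47 = 6.4%, a rising line.

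**Step 4: protocol against SAP.** Protocol 9.4.4 names laboratory parameters, vital signs, physical examinations and neurological examinations, then adds shift plots. SAP 5.6 names the first three and stops. Neither neurological examinations nor shift plots appear anywhere else in the SAP text.

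**The case against.** The strongest reply is that the signal is available elsewhere, and most of that stands.

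- The shift plots are an addition to a planned summary and listing, which can show an item still abnormal at the end of treatment.
- Section 8.2.2.1 codes each abnormality as pre-existing or new, which is itself a comparison with the pre-treatment state. Appendix 6 does not repeat the split, so this safeguard is less firm than it looks.
- Section 8.2.2 requires clinically significant findings during the trial to be recorded as AEs. Table 8-1 makes CNS-related AEs events of special interest, the AE outcome categories include not recovered, and all treatment-emergent AEs are listed.

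A reader might infer that a lasting deficit would be hidden. The documents do not support that: it appears as worsening at onset, and the routes above can show that it persists. A reader might also infer that the shift plots are the trial's only analysis bearing on the PEG risk. They are not: CNS-related and renal AESIs and PEG plasma concentration (Appendix 2) bear on it too. The accurate description is the only planned neurological shift display.

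A further reply is that the protocol labels the comparison as consecutive, takes the approach from a cited method and tests no hypothesis, so this is a preference. It is indeed descriptive, and the plots are not wrong for showing change within an interval. The reply that the panels can be summed is right for the net count only, as Step 2 shows.

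On the SAP, a reader might infer that no neurological output would be produced. That is not established. The 'such as' phrasing is open-ended, and the mock TFL may specify the outputs.

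**Conclusion.** The point holds as a weakness of the trajectory display. Under the consecutive rule a persisting new deficit is shown as worsening only at onset, and later panels cannot separate it from stable normal or pre-existing abnormal findings. This follows from the class definitions and needs no assumption about event rates.

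The illustration (a flat 2.1% per panel against 2.1%, 4.3% and 6.4% from baseline) rests on an invented accrual pattern in one patient with all 47 items evaluated. It shows the direction of the difference, not an expected size. The plots count items, so a contrast in numbers of patients taken from the last panel would use the wrong unit.

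The SAP gap is literal: the supplied text, based on protocol version 1.0, does not specify the neurological analyses of version 2.0. Whether they would nonetheless be produced cannot be decided from the documents.

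No efficacy result is affected. The change is worth making because it improves the reporting of a named potential risk from data already collected.

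**What to change.** In Protocol 9.4.4 and SAP 5.6, add for each item the shift from baseline (Visit 2) to each later examination and to the last on-treatment examination. Keep the consecutive plots as supportive. Update the SAP to protocol version 2.0, so that it names the summary, the listing and both shift presentations of the neurological examination.

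Two details can be settled in the same edit. State how items recorded as not evaluated, corrected (visual acuity) or not applicable (Romberg sign) are classed, because the three shift classes do not cover them and the denominators depend on it. Make Appendix 6 and Section 8.2.2.1 agree on whether abnormal findings are split into pre-existing and new.

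The baseline shift costs one extra table and a short SAP edit. It needs no new data and no change to any patient procedure.

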#### **9.4.5 Other analyses**

##### **Surgery**

Surgery information (surgery details, haemostatic response, consumption of nonacog beta pegol, blood loss, etc) will be listed.

#### **9.5 Interim analyses**

No interim analysis is planned.

## 10 Supporting documentation and operational considerations

### 10.1 Appendix 1: Regulatory, ethical, and trial oversight considerations

#### 10.1.1 Regulatory and ethical considerations

This trial will be conducted in accordance with the protocol and with the following:

- Consensus ethical principles derived from international guidelines including the Declaration of Helsinki and applicable ICH Good Clinical Practice (GCP) Guideline.
- Applicable laws and regulations.
- The protocol, informed consent form, investigator's brochure (as applicable) and other relevant documents (e.g. advertisements) must be submitted to an IRB/IEC and reviewed and approved by the IRB/IEC before the trial is initiated.
- Regulatory authorities will receive the clinical trial application, protocol amendments, reports on SAEs, and the CTR according to national requirements. For China, an international cooperative relevant report of related China's Human Genetic Resources will be submitted based on local regulation requirement.
- Any amendments to the protocol will require IRB/IEC approval before implementation of changes made to the trial design, except for changes necessary to eliminate an immediate safety hazard to trial patients.
- Before a site is allowed to start screening patients, written notification from Novo Nordisk must be received.

The investigator will be responsible for:

- providing written summaries of the status of the trial annually or more frequently in accordance with the requirements, policies, and procedures established by the IRB/IEC and/or regulatory authorities.
- notifying the IRB/IEC of SAEs or other significant safety findings as required by IRB/IEC procedures.
- providing oversight of the conduct of the trial at the site and adherence to requirements of ICH guidelines, the IRB/IEC, and all other applicable local regulations.
- ensuring submission of the CTR synopsis to the IRB/IEC.
- reporting any potential serious breaches to the sponsor immediately after discovery.

#### 10.1.2 Financial disclosure

Investigators and sub-investigators will provide Novo Nordisk with sufficient, accurate financial information as requested to allow Novo Nordisk to submit complete and accurate financial certification or disclosure statements to the appropriate regulatory authorities. Investigators are responsible for providing information on financial interests during the course of the trial and one year after completion of the trial.

#### 10.1.3 Informed consent process

- The investigator or his/her representative will explain the nature of the trial to the patient, the patient's LAR and/or the patient's caregiver and answer all questions regarding the trial. This includes the use of an impartial witness where required according to local requirements.

- The investigator must ensure the patient ample time to come to a decision whether or not to participate in the trial.
- Patients must be informed that their participation is voluntary.
- Patients must be informed about their privacy rights.
- Patients or their LAR will be required to sign and date a statement of informed consent that meets the requirements of local regulations, ICH guidelines, Declaration of Helsinki and the IRB/IEC or site.
- The medical record must include a statement that written informed consent was obtained before any trial related activity and the date when the written consent was obtained. The authorised person obtaining the informed consent must also sign and date the informed consent form before any trial related activity.
- The responsibility of seeking informed consent must remain with the investigator, but the investigator may delegate the task to a medically qualified person, in accordance with local requirements.
- Patients or their LAR must be re-consented to the most current version of the informed consent form(s) during their participation in the trial.
- A copy of the informed consent form(s) must be provided to the patient or the patient's LAR.
- If the minor reaches legal age while participating in the trial and has only signed an age specific informed assent form, the patient has to re-consent to an informed consent form for patients reaching legal age.

#### **10.1.4 Information to patients during trial**

The site will be offered a communication package for the patient during the conduct of the trial. The package content is issued by Novo Nordisk. The communication package will contain written information intended for distribution to the patients. The written information will be translated and adjusted to local requirements and distributed to the patient at the discretion of the investigator. The patient may receive a 'Thank you for your participation letter' after completion of the trial. Further, the patient may receive other written information during the trial.

All written information to patients must be sent to IRB/IEC for approval/favourable opinion and to regulatory authorities for approval or notification according to local regulations.

#### **10.1.5 Data protection**

- Patients will be assigned a 6-digit unique identifier, a patient number. Any patient records or datasets that are transferred to Novo Nordisk will contain the identifier only. No direct identifiers from the patient are transferred to Novo Nordisk.
- The patient and any biological material obtained from the patient will be identified by patient number, visit number and trial ID. Appropriate measures such as encryption or leaving out certain identifiers will be enforced to protect the identity of patients as required by local, regional and national requirements.
- The patient and/or the patient's LAR must be informed about the patient's privacy rights, including that his personal trial related data will be used by Novo Nordisk in accordance with local data protection law. The disclosure of the data must also be explained to the patient and/or the patient's LAR.

- The patient and/or the patient's LAR must be informed that the patient's medical records may be examined by auditors or other authorised personnel appointed by Novo Nordisk, by appropriate IRB/IEC members, and by inspectors from regulatory authorities.

## **10.1.6 Committees structure**

### **10.1.6.1 Novo Nordisk safety committee**

Novo Nordisk will perform ongoing safety surveillance. If new safety signals are identified, these will be evaluated by an internal safety committee.

If anaphylactic reactions occur in 2 patients after trial product administration, enrolment of additional patients will be put on hold. All investigators will be informed in writing. An urgent Novo Nordisk safety committee meeting will be called for to decide whether or not the trial can continue with or without modifications. During this evaluation, the trial will be on hold meaning no new patients will be recruited. Dosing of patients on treatment may continue while further evaluation of the anaphylactic reactions is made by the Novo Nordisk safety committee unless otherwise decided by the Novo Nordisk safety committee.

## **10.1.7 Dissemination of clinical trial data**

Information of the trial will be disclosed at chinadrugtrials.org.cn, clinicaltrials.gov, www.clinicaltrialsregister.eu, and novonordisk-trials.com. It will also be disclosed according to other applicable requirements, such as those of the International Committee of Medical Journal Editors (ICMJE), the Food and Drug Administration Amendment Act (FDAAA), European Commission Requirements and other relevant recommendations or regulations. If a patient requests to be included in the trial via the Novo Nordisk e-mail contact at these web sites, Novo Nordisk may disclose the investigator's contact details to the patient. As a result of increasing requirements for transparency, some countries require public disclosure of investigator names and their affiliations.

The primary completion date (PCD) is the last assessment of the primary endpoint, and is for this trial last patient first treatment + 50 weeks corresponding to visit 10 (end of treatment visit). If the last patient is withdrawn early (i.e. withdraws informed consent), the PCD is considered the date when this last patient would have completed visit 10. The PCD determines the deadline for results disclosure at clinicaltrials.gov according to FDAAA.

## **10.1.8 Data quality assurance**

### **10.1.8.1 Case report forms**

- Novo Nordisk or designee is responsible for the data management of this trial including quality checking of the data.
- All patient data relating to the trial will be recorded on electronic CRFs unless transmitted electronically to Novo Nordisk or designee (e.g. laboratory data). The investigator is responsible for verifying that data entries are accurate and correct by physically or electronically signing the eCRF.
- The following will be provided as paper CRFs to be used when access to the eCRF is revoked or the eCRF is temporarily unavailable:

- AE forms
- Safety information forms
- Technical complaint forms (also to be used to report complaints on trial product not yet allocated to a subject)
- Corrections to the eCRF data may be made by the investigator or the investigator's delegated staff. An audit trail will be maintained in the eCRF application containing as a minimum: the old and the new data, identification of the person entering the data, date and time of the entry and reason for the correction. If corrections are made by the investigator's delegated staff after the date when the investigator signed the eCRF, the eCRF must be signed and dated again by the investigator.
- The investigator must ensure that data is recorded in the eCRF as soon as possible, preferably within 5 working days after the visit. Once data has been entered, it will be available to Novo Nordisk for data verification and validation purposes.

